10.3.2.1 Elective Surgery/Routine Examination

Elective surgery (a planned, non-emergency medical procedure) and in-patient routine examination for a pre-existing condition (i.e., recorded in the medical history) do not qualify as SAEs as long as the procedure was not performed as a result of a worsening of the condition. However, AEs which occur during any elective hospitalisation will need to be collected and reported.

10.3.3 Pregnancy

When a female subject becomes pregnant during the study and study treatment has been administered to the subject, the outcome of the pregnancy needs to be monitored and the safety of the mother and unborn child need to be safeguarded (as per protocol, pregnancy is an exclusion criteria). Therefore, the outcome of all such pregnancies (including normal births) must be followed up and documented, even if the subject was withdrawn from the study or the study has been completed.

Women of childbearing potential should have a negative serum pregnancy test prior to randomisation. Study treatment should not be initiated by the Investigator until a report of a negative pregnancy test has been obtained.

A highly effective contraception must be used in female subjects of childbearing potential before beginning study treatment, during study dosing, and for 30 days following discontinuation of study treatment.

Following sections in italics are applicable for United Kingdom only (**UK only**):

Highly effective birth control methods include:

- *Combined (oestrogen and progestogen containing) hormonal contraception associated with inhibition of ovulation*

- *Oral*
- *Intravaginal*
- *Transdermal*
- *Progestogen-only hormonal contraception associated with inhibition of ovulation*
 - *Oral*
 - *Injectable*
 - *Implantable*
- *Intrauterine device*
- *Intrauterine hormone-releasing system*
- *Bilateral tubal occlusion*
- *Vasectomised partner*
- *Sexual abstinence*

Due to the follow-up of 52 weeks per patient after randomisation in the present study, sexual abstinence is only acceptable as 'true abstinence' when this is in line with the preferred and usual lifestyle of the subject. Periodic abstinence (e.g., calendar, ovulation, symptothermal, post-ovulation methods), declaration of abstinence for the duration of exposure to IMP, and withdrawal are not acceptable methods of contraception.

A female subject must immediately inform the Investigator if she becomes pregnant during the study and no further study treatment shall be administered. The Medical Monitor must be contacted immediately to break the blind (if applicable). The Investigator should counsel the subject and discuss the risks of continuing with the pregnancy and the possible effects on the foetus.

The Investigator/Sponsor is responsible for monitoring the subject and pregnancy outcome. Every effort should be made to gather information regarding the pregnancy outcome until 90 days postpartum (or otherwise as appropriate). It will be the responsibility of the Sponsor, together with the appropriate support of the Investigator, to obtain this information.

Any report of pregnancy recorded for any female subject should be reported to the CRO/Vifor Pharma within the same timelines as a SAE, i.e., immediately (within 24 hours of awareness). The Investigator should complete a Vifor Pharma Report on Exposure to Medicines During Pregnancy form (see [Appendix 2](#)) and forward to the CRO/Vifor Pharma. Complications of pregnancy such as abortion (spontaneous or

induced), premature birth (before 37 weeks gestational age) or congenital abnormality are considered SAEs and should be reported using the study-specific Vifor Pharma SAE form.

All pregnancies occurring in a female subject within 90 days after discontinuation of investigational product should be reported within the same timelines as a SAE to the CRO/Vifor Pharma.

11. STUDY COMMITTEES

11.1 DSMB/DMC Procedures

A DSMB/DMC will be constituted to protect the safety of study participants. A DSMB/DMC is a group of independent experts external to a study assessing the progress, safety data and, if needed critical efficacy endpoints of a clinical study. Most DSMBs/DMCs are composed of clinicians with expertise in relevant clinical specialties and at least 1 biostatistician knowledgeable about statistical methods for clinical trials and sequential analysis of trial data. For trials with unusually high risks or with broad public health implications, the DSMB/DMC may include a medical ethicist knowledgeable about the design, conduct, and interpretation of clinical trials. For practical reasons the number of members of a DSMB/DMC should be limited.

The DSMB/DMC will receive blinded eCRF data in the form of tables and listings (prepared by an independent statistician), and adjudicate on subject status changes and dosing decisions (where appropriate). Where appropriate, the DSMB/DMC may receive unblinded data (on a subject level or treatment group level) that should be reviewed in a closed session. The data should include, but is not limited to, demographics, subject enrolment, baseline characteristics, AE data, SAE data (by severity and causality), laboratory data, dose adjustments, protocol adherence, and subject withdrawals. The DSMB/DMC will evaluate the progress of the trial, assess data quality and timeliness, participant recruitment, accrual and retention, and participant benefit/risk. In addition the DSMB/DMC will monitor external factors relevant to the trial, for example scientific and therapeutic developments that may affect participant safety or ethical status. Based on the observed benefits or adverse effects, the DSMB/DMC will make recommendations to the Sponsor concerning continuation, termination or modifications of the trial.

The Sponsor will establish a charter document explaining the working procedures and responsibilities of the DSMB/DMC. The charter should be agreed to by the DSMB/DMC.

11.2 Steering Committee

The Steering Committee (SC), chaired by Co-ordinating Investigator, will be responsible for maintaining the scientific integrity of the trial. Members will be selected investigators from the participating countries/regions. The Co-ordinating Investigator will review and approve the trial protocol and subsequent protocol amendments, taking into account also feedback from other SC members, if applicable. The SC will be blinded to study treatment allocation while the trial is ongoing. Each SC member is expected to discuss with the SC Chairman any activities that might constitute a conflict of interest for the AFFIRM-AHF trial.

SC meetings will be attended by, in addition, representatives of the Sponsor and coordinating personnel (if applicable), in a non-voting capacity.

11.3 Clinical Endpoint Committee

An independent CEC will be formed to adjudicate all events suggestive of the study endpoints using prospectively defined criteria which will be detailed in the CEC charter. Members of the CEC will not be employees of Sponsor. This committee will be composed of at least three members including at least one cardiologist specialising in HF. The CEC will adjudicate the events blinded to study treatment group allocation. Endpoint adjudication will be done, using a web-based adjudication system, on an ongoing basis throughout the duration of the trial. The adjudicated events will be used for the analyses of the primary endpoint, secondary and other endpoints.

12. STATISTICAL ANALYSIS

12.1 Statistical Methods

All statistical analyses will be performed using SAS Version 9.3 or later (SAS Institute Inc. SAS/STAT, Cary, NC, United States). The level of significance to be used will be 0.05. Detailed methodology for summary and statistical analyses of the data collected in this trial will be documented in a Statistical Analysis Plan (SAP), which will be finalised prior to unlocking of the study data base. A general description of the planned methods is provided below. Any deviation from the SAP will be noted and explained in the final study report.

12.2 Sample Size and Power Calculations

The recurrent HF hospitalisation and CV death rates in the control group was extrapolated as 0.9 events/year using the data from the EVEREST study [37] and as 0.61 events/year using the data from the ESC-HF study [38]. For this study, it is anticipated that approximately 35% of subjects will sustain either a CV death or will sustain at least one HF hospitalisation. It is also anticipated that 12% of subjects will sustain a CV death. Assuming that 50% of subjects who sustain a CV death will not undergo any prior HF hospitalisation and that the average number of HF hospitalisations per subject with at least one HF hospitalisation will be estimated as 2, the number of events per 100 years has been estimated as follows: 12 CV deaths + 2*(35-6) HF hospitalisations, which equates to approximately 70 events/100 years of follow-up for HF hospitalisations and CV death.

Concerning the event rate ratio, it is assumed that there will be a 30% reduction in HF hospitalisations for subjects allocated to FCM and that CV death rates will be similar between the FCM and placebo groups. It is therefore assumed that the rate ratio between FCM and placebo for the composite of recurrent HF hospitalisations and CV deaths will be approximately 25%.

The dispersion factor used in negative binomial regression is a measure of the mean-variance. There is currently insufficient data to estimate the negative binomial dispersion. For this sample size calculation, a dispersion factor (K) of 1 was assumed.

The sample size calculation was done in the software NCSS PASS-14 [39] using the sample size formula proposed by Zhu and Lakkis 2014 [40] to compare two negative binomial rates.

Assuming a recurrent HF hospitalisation and CV death of 0.7 events/year the placebo group, in total, 1,000 subjects (500 per study treatment group) would be required to demonstrate a statistically significant rate ratio of 0.75 (i.e., 25% reduction of recurrent events between the FCM and placebo groups) with a power of 80% and a 2-sided alpha of 0.05. Taking into account 9% loss to follow-up, a sample size of 1,100 subjects (550 per treatment group) is planned.

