- Subjects for whom an administration of study treatment is necessary during an outpatient clinic visit will be requested to return to the outpatient clinic for the administration of study treatment maximally 7 days after the date when the blood sample was performed.
- Study treatment will be prepared and administered by unblinded study personnel as described in the 'Treatment' section.
- If ID persists at Week 52 (Visit 6), the Investigator will treat the ID according to local routine/standard practice.
- Subjects will be contacted by telephone at Weeks 2, 4 and 36 after randomisation – see Table 2.

	
* Following section in italics is applicable for The Netherlands, Spain and Singapore only (NL, ES and SG only):
 
The lower threshold of Hb values is set to 10 g/dL.
 
Study Committees and Trial Oversight
 
A Steering Committee (SC), a Data Safety Monitoring Board (DSMB) and a Clinical Endpoint Committee (CEC) will be established for this trial.
 
The SC will ensure the scientific integrity of the trial in addition to overseeing the operational conduct. The DSMB will be constituted to oversee the safety of study participants and the CEC will adjudicate all events suggestive of the study outcomes using predefined criteria detailed in the adjudication charter.

Sample Size:	
A total of 1,100 subjects is planned to be randomised (i.e., 550 per treatment group). Using the negative binomial statistical approach, the study would require 1,000 subjects in total (500 per study group) for a power of 80% and a 2-sided alpha of 0.05 to demonstrate a statistically significant rate ratio of 0.75 (i.e., 25% reduction in the composite of recurrent HF hospitalisations and CV death, between the FCM and placebo groups) assuming a recurrent event rate of 0.7 events/year for HF hospitalisations and CV death in the placebo group. The mean follow-up time is estimated to 11 month accounting for a death rate of 12%. Taking into account loss to follow-up, an overall sample size of 1,100 subjects (550 per treatment group) is planned.

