12.7 Efficacy Evaluations

12.7.1 Primary

The primary outcome is the composite of recurrent HF hospitalisations and CV death up to 52 weeks after randomisation.

The HF hospitalisation and CV death rates per 100 patient-years of follow-up as adjudicated by the CEC, will be calculated by dividing the total number of HF hospitalisations, and CV deaths by the total follow-up duration of all subjects in each group. The rate ratio (95% CI and p-value) for this analysis will be analysed using a negative binomial model. Compared to the Poisson distribution, the negative binomial

distribution allows for different individual tendencies (frailties) with respect to their risks of repeat hospitalisations [41].

The negative binomial model will be adjusted for the following baseline covariates: sex, age, HF aetiology (ischemic/non-ischemic), HF duration (newly diagnosed at Index hospitalisation/known documented HF prior to Index hospitalisation) and country. A sensitivity analyses will be performed using an unadjusted model.

The primary outcome analysis will be performed on the FAS will use the CEC adjudicated events. A sensitivity analysis will be performed on the PP population set.

Descriptive statistics will provide, per treatment group, the total number of events and the number (%) of subjects with at least one event.

A graphical representation of the estimated cumulative hazard rate will also be provided.

As the analysis of HF hospitalisations could be confounded by the competing risk of death, a confirmatory analysis will be performed on the FAS population set using the joint frailty model in order to analyse repeat hospitalisation rate whilst accounting for their associated mortality rate [42].

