4. STATISTICAL METHODS

4.1. Sample Size Justification

The recurrent HF hospitalisation and CV death rates in the control group were extrapolated as 0.9 events/year using the data from the EVEREST study [3] and as 0.61 events/year using the data from the ESC-HF study [4]. For this study, it is anticipated that approximately 35% of subjects will sustain either a CV death or at least one HF hospitalisation. It is also anticipated that 12% of subjects will sustain a CV death. Assuming that 50% of subjects who sustain a CV death will not undergo any prior HF hospitalisation and estimating the average number of HF hospitalisations per subject with at least one HF hospitalisation as 2, the number of events per 100 years of follow-up has been estimated as follows: 12 CV deaths + 2*(35-6) HF hospitalisations, which equates to approximately 70 events/100 years of follow-up for HF hospitalisations and CV death.

Concerning the event rate ratio, it is assumed that there will be a 30% reduction in HF hospitalisations for subjects allocated to FCM and that CV death rates will be similar between the FCM and placebo groups. It is therefore assumed that the rate ratio between FCM and placebo for the composite of recurrent HF hospitalisations and CV deaths will be approximately 25%.

The dispersion factor used in negative binomial regression is a measure of the mean-variance. There are currently insufficient data to estimate the negative binomial dispersion. For this sample size calculation, a dispersion factor (K) of 1 was assumed.

The sample size calculation was done in the software NCSS PASS-14 [5], using the sample size formula proposed by Zhu and Lakkis 2014 [6] to compare two negative binomial rates.

Assuming a rate of recurrent HF hospitalisation or CV death of 0.7 events/year in the placebo group, a total of 1,000 subjects (500 per study drug group) would be required to demonstrate a statistically significant rate ratio of 0.75 (i.e., 25% reduction of recurrent hospitalisations or deaths between the FCM and placebo groups) with a power of 80% and a 2-sided alpha of 0.05. Taking into account an expected 9% loss to follow-up, a sample size of 1,100 subjects (550 per treatment group) is planned.

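### The 80% power at 1,000 subjects is conditional on K=1, which is optimistic against the plan's own 35% with an event and 0.7 events/year, and no sensitivity to K is shown

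*Protocol*

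**What the plan says.** Protocol 12.2 and SAP 4.1 carry the same derivation. In the protocol's words, "it is anticipated that approximately 35% of subjects will sustain either a CV death or will sustain at least one HF hospitalisation". CV death is put at 12%, half of those deaths without a prior HF admission, and "the average number of HF hospitalisations per subject with at least one HF hospitalisation will be estimated as 2". The sum 12 + 2×(35−6) follows, "which equates to approximately 70 events/100 years of follow-up for HF hospitalisations and CV death", and 0.7 events/year is assigned to the placebo group.

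On dispersion, SAP 4.1 says: "There are currently insufficient data to estimate the negative binomial dispersion". Both documents then continue: "For this sample size calculation, a dispersion factor (K) of 1 was assumed".

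The protocol synopsis gives the result: "the study would require 1,000 subjects in total (500 per study group) for a power of 80"%, at a two-sided alpha of 0.05 and a rate ratio of 0.75. It also gives the only follow-up figure: "The mean follow-up time is estimated to 11 month accounting for a death rate of 12"%. The step to 1,100 is for 9% loss to follow-up.

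For the primary analysis, Protocol 12.7.1 says: "The negative binomial model will be adjusted for the following baseline covariates", namely sex, age, HF aetiology, HF duration and country. Neither document shows power at any other K.

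**The concern.** In a negative binomial model, the mean and K together determine the share of subjects with at least one event. The plan supplies a mean and a share and then chooses K separately, so the three can be checked against each other. They do not agree: K=1 puts more subjects in the event group than the 35% from which the rate was built. For a fixed mean, a smaller share with an event means more clustering, a larger K and less power.

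At stake is the stated 20% chance of missing a true 25% reduction, and so how a non-significant primary result would be read. No interim analysis is planned (Protocol 12.9, SAP 4.3), and I found no blinded re-estimation of dispersion that would correct a poor choice of K.

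**Working it through.** **Inputs.** Placebo rate 0.7/year, rate ratio 0.75, K=1, 35% with an event, 12% CV death, mean 2 admissions (Protocol 12.2, SAP 4.1); mean follow-up 11 months (synopsis).

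**1. The plan's figure.** Zhu-Lakkis: n per arm = (1.96√V0 + 0.842√V1)² / (ln 0.75)², with V1 = (1/0.7 + 1/0.525)/t + 2K. V0 is 2/(0.7t) + 2K (reference-rate form) or V1 (true-rate form).
- K=1, t=11/12, reference rate: V0 = 5.117, V1 = 5.636, n = 499.8 per arm. This is the plan's 1,000.
- K=1, t=1: 474.0 per arm (reference rate, 82% power at 500) or 505.8 (true rate, 79.5%).
- 1,000/0.91 = 1,099, and (12 + 0.7×58)/70 = 0.751. The 1,100 and the 0.75 also reproduce.

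**2. Share with an event under K=1.** P(at least one) = 1 − (1+Kμ)^(−1/K).
- 12 months, μ = 0.70: 0.70/1.70 = 41.2%.
- 11 months, μ = 0.7×11/12 = 0.642: 0.642/1.642 = 39.1%.

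**3. K that matches 35%, and the power.** Solve (1+Kμ)^(−1/K) = 0.65 for the placebo arm, or set the average of the two arms (FCM mean 0.75μ) to 35%. Power = Φ((√n·|ln 0.75| − 1.96√V0)/√V1).

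| Reading of 35% | Follow-up | K | Power at 1,000, reference / true rate | At 1,100 |
|---|---|---|---|---|
| Placebo arm | 11 months | 1.74 | 70.0 / 67.4% | 73.9 / 71.5% |
| Placebo arm | 12 months | 2.10 | 67.3 / 65.0% | 71.3 / 69.1% |
| Both arms | 11 months | 1.15 | 77.9 / 75.2% | 81.5 / 79.1% |
| Both arms | 12 months | 1.51 | 74.7 / 72.3% | 78.5 / 76.3% |

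**4. Rounding of the 35%.** With 37% or 38% in the placebo arm, the same equations give K from 1.69 down to 1.18 and power of about 70-78% at 1,000.

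**5. The build-up without assuming a negative binomial.** Take 6% with CV death only, 6% hospitalised with CV death, 23% hospitalised only, and H admissions per hospitalised subject with mean 2. The moment value is K = (0.29·E[H²] + 0.24 + 0.12 − 0.49 − 0.70)/0.49. The unadjusted negative binomial was fitted by maximum likelihood to simulated trials with full follow-up and the 30% reduction applied per admission (4,000 trials each, Monte Carlo SE about 0.7 points).

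| Admissions if hospitalised | Moment K | Median fitted K | Power at 1,000 / 1,100 |
|---|---|---|---|
| Exactly two | 0.67 | 1.23 | 77.9 / 82.0% |
| 1+Binomial(2, 0.5) | 0.97 | 1.50 | 74.6 / 77.9% |
| 1+Poisson(1) | 1.27 | 1.67 | 70.4 / 75.6% |
| Geometric | 1.86 | 1.89 | 66.3 / 72.1% |

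Applying the reduction per patient instead gives 63-72% at 1,000.

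**6. Check of the formula.** On true negative binomial counts (5,000 trials, 500 per arm), simulated power was 77.5% for K=1 at 11 months, 69.3% for K=1.74 at 11 months and 64.6% for K=2.10 at 12 months.

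**The case against.** The strongest reply is that this is a disclosed assumption and not an error of arithmetic. That stands: 1,000 is right given K=1, and the plan says that it could not estimate K. A reader might infer that the sample size was miscalculated; step 1 shows that it was not.

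Second, K is not a quantity that the plan's inputs fix. No variance is given, the composite is not exactly negative binomial, and moment-based K is below 1 if admissions per hospitalised subject vary little. This also stands, so 65-70% cannot be presented as the trial's true power. But the primary analysis fits a negative binomial model, and even in those two low-variance cases the fitted K exceeds 1 and power is about 74-78%.

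Third, the 35% is approximate and names no arm. As a both-arms average at 11 months, K=1 implies (39.1 + 32.5)/2 = 35.8%, which nearly closes the gap. This reading is weaker, because the 35% is what builds the rate assigned to placebo, but the text does not exclude it. For the same reason, a reader should not infer that power comes near 80% only if every hospitalised subject has exactly two admissions: the both-arms reading reaches 77.9% too.

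Fourth, all these K values are unadjusted, and covariates can lower residual dispersion. With 1+K = (1+K_residual)(1+CV²), reaching a residual K of 1 needs CV² of 0.371 (from 1.74) or 0.549 (from 2.10). Assuming a lognormal risk score, that is a log-rate SD of 0.56-0.66, or a 3.1- to 3.8-fold rate difference between subjects 1 SD above and below the mean. From K=1.15 an SD of 0.27 is enough. The documents give no prognostic strength for the covariates, so the point stays open.

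Finally, step 6 shows the formula running about 2.5 points high at K=1 and 11 months, so a small part of a simulated shortfall from 80% reflects the approximation and not K.

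**Conclusion.** The point holds as a conflict between inputs in one section. Against about 35% with an event and 0.7 events/year, K=1 is optimistic and the 80% is overstated. On the natural placebo-arm reading, the chance of missing a true 25% reduction at 1,000 subjects is about 30-35%, not 20%; on the both-arms reading it is about 22-28%. At 80% power, the detectable ratio under the placebo-arm K is about 0.71-0.72 instead of 0.75.

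The size depends on which arm the 35% describes, how exact it is, how admissions are distributed, and how much the covariates explain. The direction is less sensitive: every unadjusted maximum-likelihood fit and every match to 35% gave K above 1. A reader might go further and conclude that K is known to be 1.7-2.1, or that enrolment had to rise. The documents support neither, because they do not determine K. The treatment estimate and its confidence interval are untouched. This should be corrected, with medium confidence in the exact figures.

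**What to change.** In Protocol 12.2 and SAP 4.1, keep the derivation of 1,000. State that the 80% is conditional on K=1, that this is optimistic against 35% and 0.7/year, and that K is unadjusted for covariates. Add a table for the pairing that reproduces the plan (11 months, reference-rate variance, formula in step 1):

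| K | Placebo subjects with an event | Power at 1,000 | Power at 1,100, full contribution |
|---|---|---|---|
| 1.0 | 39% | 80.0% | 83.5% |
| 1.25 | 38% | 76.5% | 80.2% |
| 1.5 | 36% | 73.1% | 77.0% |
| 1.75 | 35% | 69.9% | 73.8% |
| 2.1 | 33% | 65.7% | 69.7% |

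If 12-month rows are added, label them as a separate pairing, since with this variance they start from 82% at K=1. State beside the table that power at 1,000 is about 65-70% on the placebo-arm reading, across follow-up pairings and variance forms, and about 72-78% on the both-arms reading.

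Alternatively, keep K=1 and 80%, change the 35% to about 39-41%, and justify it. Mean admissions must then fall to 58/(39.1−6) = 1.75 or 58/(41.2−6) = 1.65 to keep the build-up at 70 per 100; left at 2, it gives 78 or 82.

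The synopsis states no K, so only its power statement needs the matching qualification. The cost is a qualified power claim and one short table, with no extra patients, visits or data.
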